CONFIDENTIAL - PROTOCOL

The following contains confidential, proprietary information which is the property of Recros Medica

The CONFORM Study: A Multi-Center Study to Evaluate the Safety and Efficacy of Rotational Fractional Resection on Submental Contouring

Protocol Number:	CLP-0002
Version	18-October-2018 (Amendment 3)
Name of Investigational Product:	Recros Medica Focal Contouring System
Sponsor:	Recros Medica, Inc. [name]
NCT Number	NCT03407313

Investigational Device:

Recros Medica Focal Contouring System to perform Rotational Fractional Resection (skin resection and focal lipectomy)

Study Objective:

The objective is to evaluate the efficacy and safety of using Rotational Fractional Resection in improving submental contouring.

Clinical Hypotheses:

Primary Efficacy:

Removal of skin and fat using Rotational Fractional Resection will result in a noticeable improvement of submental contour, as determined by a mean 0.75 grade improvement on either the Submental Skin Laxity Scale or Submental Lipodystrophy Scale.

Primary Safety:

Post-procedure scarring will be assessed using the Manchester Scar Scale.

Study Design

Structure: Prospective, multi-center, single-arm (non-randomized), interventional cohort, non-significant risk (NSR) study

Duration: Approximately 7 months for each subject from the screening visit to the exit visit.

Visit Schedule: Screening, procedure, Day 1, 7, 14, 30, 90 and 180 post-procedure.

Indication for Use: The Recros Medica focal contouring system is intended for resecting skin and removing fat for the purpose of focal aesthetic contouring of the submentum.

Study Population Characteristics

Number of Subjects: Up to approximately 110 subjects will be enrolled into this study to ensure up to approximately 70 subjects treated at approximately 4-8 investigational sites in the US to ensure that there are at least 55 evaluable subjects.

Condition/Disease: Adult subjects with mild to moderate submental fat and mild to moderate submental skin laxity.

Key Inclusion Criteria: Healthy male or female, at least 30 years old; mild to moderate submental lipodystrophy; mild to moderate submental skin laxity; Fitzpatrick skin phototype 1, 2 or 3; agree to maintain weight (5%) for the duration of the study

Key Exclusion Criteria: History of any intervention to treat submental fat or skin laxity (e.g., liposuction, surgery, chemical lipolysis, cryolipolysis); history of psoriasis, hyperpigmentation, eczema, rosacea or vitiligo; history of keloids, hypertrophic scarring, or other skin condition that may result in excessive scarring; history of folliculitis in hirsute areas; body mass index >30 kg/m²; treatment with aspirin or aspirin containing products (e.g., Excedrin), NSAIDS, vitamin E within 14 days of the procedure.

Response Measures

Primary Efficacy:

- Submental Skin Laxity Scale, as assessed by independent raters
- Submental Lipodystrophy Scale, as assessed by independent raters

Secondary Efficacy:

- Submental Skin Laxity Scale, as assessed by the investigator
- Submental Lipodystrophy Scale, as assessed by the investigator
- Subjects with at least a 1-point improvement on the Submental Skin Laxity or Lipodystrophy Scales, as assessed by independent raters
- Subject Satisfaction Questionnaire, as assessed by the subjects
- Image Analysis (IA) of facial photography for skin laxity
- Pre- and post-procedure photography comparison, as assessed by independent raters

Primary Safety:

• Manchester Scar Scale

Secondary Safety:

- Adverse events
- Visible scarring
- Visual skin assessment in procedure area by the investigator and the subject
- Pain assessment, using an 11-point Numeric Rating Scale (0 to 10), as assessed by the subject
- Vital signs (blood pressure and pulse rate)

Sample Size Calculation and Analysis Methods:

The sample size calculation is based on two t-tests of the hypotheses for the primary efficacy endpoints. One endpoint is the change in the Skin Laxity Scale from baseline to 90 days; the other is the change in the Skin Lipodystrophy Scale from baseline to 90 days. The null hypotheses are that there is no change in the scale scores. The alternative hypotheses is that there is a change of at least 0.75 points on at least one scale. The endpoint is a composite endpoint of the two, with the requirement for passing the Primary Efficacy Hypothesis that at least one of the null hypotheses be rejected.

Assuming that the true change is 1.0 points on each test, and that the standard deviation (SD) is 0.7 points, the sample size required for combined power of 91% and Type 1 error of 5% is 55. The sample size calculation was done with PASS 14^{1} for an inequality test of one mean.

To accommodate approximately 10% attrition, the number of subjects undergoing the procedure will be $55/.9 \approx 60$.

¹ PASS 14 Power Analysis and Sample Size Software (2015). NCSS, LLC. Kaysville, Utah, USA, ncss.com/software/pass.

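### Either of two primary t-tests can pass the trial, but the single 5% Type 1 error has no per-test level, sidedness or multiplicity rule, so 5% overall is not secured

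*Combined protocol and SAP*

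**What the plan says.** All of this is in the Combined protocol and SAP.

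- **Tests.** Sample Size Calculation and Analysis Methods defines two primary t-tests on the change from baseline to 90 days, one for skin laxity and one for lipodystrophy.
- **Pass rule.** The pair is given one label, "The endpoint is a composite endpoint of the two", and one rule, "with the requirement for passing the Primary Efficacy Hypothesis that at least one of the null hypotheses be rejected".
- **Hypotheses.** The null is "The null hypotheses are that there is no change in the scale scores". The alternative is "The alternative hypotheses is that there is a change of at least 0.75 points on at least one scale".
- **Claim.** Under Clinical Hypotheses, Primary Efficacy, the effect is directional and has a size: "as determined by a mean 0.75 grade improvement on either the Submental Skin Laxity Scale or Submental Lipodystrophy Scale".
- **Error and power.** With a true change of 1.0 on each scale and SD 0.7, "the sample size required for combined power of 91% and Type 1 error of 5% is 55". The software procedure is described only as being "for an inequality test of one mean".

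No per-test level, sidedness, alpha split, testing order or correlation between the scales is given.

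**The concern.** A rule that passes on either of two tests gives the trial two chances to succeed by luck. One 5% figure can describe such a rule only if the plan says how the 5% is shared, or that it is the overall level. Calling the pair a composite does not help: there are two nulls and two tests, with no single combined score.

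At stake is the false-pass risk of the primary claim, which could be held at 5% or could be nearly double that, depending on a choice these sections do not record. The null adds to the problem. The hypotheses are written against no change, while the claim is a 0.75 grade improvement, and the observed mean needed to pass differs greatly between the two.

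**Working it through.** **Inputs from the plan:** two tests, either sufficient; n = 55; SD 0.7; true change 1.0; Type 1 error 5%; combined power 91%; written null 0; claimed improvement 0.75.

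**Assumptions:** the correlation ρ between the two scale changes, which the plan does not give; and a null of 0.75 wherever it is used below.

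**1. Can the plan's 91% at n = 55 be reproduced?**

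One-sample t-test power comes from the noncentral t with n − 1 degrees of freedom and noncentrality (true change − null)/SD × √n. For two independent tests of equal power p, combined power is 1 − (1 − p)².

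*Written null of 0.* The difference is 1.0 and the noncentrality is 1.0/0.7 × √55 = 10.6, so power exceeds 99.9%. With two-sided 2.5% per test and independent scales, 6 subjects give 87% combined power and 7 give 94%. A sample size of 55 cannot come from this null.

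*Null of 0.75.* The difference is 0.25 and the noncentrality is 0.25/0.7 × √55 = 2.65.

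| Per-test level | One scale, p | Either scale, independent | n for 91%, independent |
|---|---|---|---|
| One-sided 5% | 0.834 | 1 − 0.166² = 97.2% | 39 |
| One-sided 2.5% (for improvement, same as two-sided 5%) | 0.739 | 1 − 0.261² = 93.2% | 51 |
| Two-sided 2.5% | 0.635 | 1 − 0.365² = 86.7% | 63 |

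None gives 91% at 55. Simulating correlated t-tests at n = 55 gives this combined power:

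| Per-test level | ρ = 0 | 0.2 | 0.5 | 0.7 |
|---|---|---|---|---|
| One-sided 5% | 97% | 96% | 94% | 91% |
| One-sided 2.5% | 93% | 91% | 87% | 84% |
| Two-sided 2.5% | 87% | 84% | 79% | 75% |

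So 91% appears at ρ of about 0.7, about 0.2, or (for two-sided 2.5%) about −0.33. Each per-test level can be made to fit by choosing a correlation, so the stated power does not identify the level used.

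**2. What is the false-pass risk?**

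With both scales at the null and independent, the risk is 1 − (1 − α)²: 1 − 0.95² = 9.75% at 5% each, and 1 − 0.975² = 4.94% at 2.5% each. Whatever the correlation, it cannot exceed 2 × 0.05 = 10% or 2 × 0.025 = 5%. Simulation at n = 55 gives:

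| Rule per test | ρ = 0 | 0.5 | 0.7 |
|---|---|---|---|
| One-sided 5%, improvement | 9.75% | 8.8% | 8.1% |
| One-sided 2.5%, or upper tail of two-sided 5%, improvement | 4.9% | 4.6% | 4.2% |
| Two-sided 5%, rejection in any direction | 9.75% | 9.1% | 8.4% |

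The last row is kept apart because a significant worsening is not an improvement. The pass rule as written does not exclude it, however.

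**3. What observed mean passes?**

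The standard error is 0.7/√55 = 0.0944. The critical values of t with 54 degrees of freedom are 1.674 (one-sided 5%), 2.005 (one-sided 2.5%) and 2.306 (two-sided 2.5%). The mean on one scale must therefore exceed the null by 0.158, 0.189 or 0.218. Against no change, an observed mean of 0.16 to 0.22 is enough. Against 0.75, it must reach 0.91 to 0.97.

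**The case against.** The best defence is that the plan leaves alpha unspecified but does not show it to be inflated. A null of no change against an alternative of change reads naturally as two-sided. Two-sided 5% per test keeps the false-improvement risk at or below 5%. The 5% also stands in the same sentence as the combined power, so an overall 5% is a fair reading. The failure to reproduce 91% is neutral, since one design that controls the error (one-sided 2.5% each, ρ about 0.2) matches it. The text is short and reads like a synopsis. Finally, the wide gap in the passing mean comes from the null, not from multiplicity.

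Much of this stands. The 8% to 10% range is the result under one reading, not the expected result. The null conflict is a distinct defect, and by itself the choice among these alpha levels moves the pass mark by only 0.03 to 0.06 grade.

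The omission is still not answered. An overall 5% needs a per-test level to deliver it, and none is given. The two-sided reading protects the claim only if rejections for worsening are excluded, which the pass rule does not say. Because the stated power fits several alpha levels equally well, it cannot stand in for the missing statement.

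**Conclusion.** The concern holds. Across the readings the text allows, the false-pass risk for improvement runs from no more than 5% to almost 10%, and nothing in the document fixes which applies. This shows that 5% is not secured; it does not show that 5% will be exceeded. The stated 91% at 55 subjects does not follow from the stated inputs. The written null would also let a mean change of about 0.2 grade on one scale pass a hypothesis framed as a 0.75 grade improvement.

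The upper bounds of 5% and 10% need no correlation assumption; the figures within them do. The power figures that compete with 91% also rest on the assumed 0.75 null. This should be fixed before analysis because it concerns the trial's primary pass rule.

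**What to change.** In Sample Size Calculation and Analysis Methods:

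1. Reconcile the null with the 0.75 grade improvement in the primary efficacy hypothesis.
2. State that only improvement counts towards passing, and whether the tests are one- or two-sided.
3. Test each scale at Day 90 at 2.5% (Bonferroni). That is sufficient for the either-scale rule. Holm is needed only if a separate claim will be made for each scale.
4. Restate combined power at n = 55 with its correlation assumption. For a 0.75 null and ρ of 0 / 0.2 / 0.5, it is 93% / 91% / 87% at one-sided 2.5% each, or 87% / 84% / 79% at two-sided 2.5% each.

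The cost is a few sentences and a revised power figure; no added subjects are proposed. One-sided 2.5% each already holds the false-improvement risk at 5%. Two-sided 2.5% each is stricter, at about 2.5% when ρ = 0, and is where most of the power loss falls. If the sponsor chose the two-sided version and still wanted 91%, 63 evaluable subjects would suffice at ρ = 0. That means 63/0.9 = 70 treated, which fits the plan's figure, "to ensure up to approximately 70 subjects treated at approximately 4-8 investigational sites". At ρ = 0.5, 63 evaluable subjects would give only 85%.

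### The 91% power for success on at least one scale is not supported as an unconditional figure: it depends on an unstated per-test alpha and correlation, and arises only if 0.75 is the tested value

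*Combined protocol and SAP*

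**What the plan says.** Under Sample Size Calculation and Analysis Methods, the protocol bases the trial's size on two t-tests, one for the 90-day change on the Skin Laxity Scale and one for the 90-day change on the Lipodystrophy Scale. Both nulls are written as zero change. The alternative is that "there is a change of at least 0.75 points on at least one scale". The primary efficacy hypothesis passes if either null is rejected.

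The inputs are given as follows: "Assuming that the true change is 1.0 points on each test, and that the standard deviation (SD) is 0.7 points". The result is that "the sample size required for combined power of 91% and Type 1 error of 5% is 55". On method, the text says only "The sample size calculation was done with PASS 14^{1} for an inequality test of one mean".

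The paragraph does not give the sidedness, the alpha for each test, the correlation between the two changes, how two tests became one power figure, or the power if only one scale improves. Under Clinical Hypotheses, the target is a mean improvement of 0.75 grade on either scale.

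**The concern.** The power to reject at least one of two tests is not fixed by the sample size, mean and SD alone. It also depends on the level of each test and on how strongly the two change scores move together within a subject. A routine "for an inequality test of one mean" handles one test at a time and takes no correlation, so a further step was needed to reach a combined figure, and that step is not described.

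A positive correlation is plausible here: both scales are graded on the same submentum of the same subjects, after one procedure that removes skin and fat. The more the changes move together, the less a second chance to pass is worth. The calculation also credits a full 1.0-point change to both scales, while the success rule needs only one to respond. The 91% is the justification for 55 evaluable subjects, so the sponsor should know under what conditions it holds.

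**Working it through.** **Inputs from the sample-size paragraph.** n = 55; SD = 0.7; true change 1.0 on each scale; threshold 0.75; nominal error 5%; success if at least one test rejects.

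**Assumptions of this check.** Correlations of 0 to 0.7 between the change scores, and the three per-test levels below. The documents give neither.

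**Step 1: the null as written (0).** The noncentrality is (1.0/0.7) × √55 = 10.59. The critical value at two-sided 2.5% with 54 degrees of freedom is 2.306. Power on one scale is essentially 100%, so the 91% cannot come from this null, whatever the correlation.

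**Step 2: 0.75 as the tested value.** The difference is 1.0 − 0.75 = 0.25, the standardised difference is 0.25/0.7 = 0.357, and the noncentrality is 0.357 × √55 = 2.649. Per-scale power from the noncentral t:
- two-sided 5% (critical value 2.005): 73.9%
- two-sided 2.5% (2.306): 63.5%
- one-sided 5% (1.674): 83.4%

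**Step 3: trying to reproduce 91%.** With independent tests, at-least-one power is 1 − (1 − p)²:
- two-sided 5%: 1 − 0.261² = 93.2%
- two-sided 2.5%: 1 − 0.365² = 86.7%
- one-sided 5%: 1 − 0.166² = 97.2%

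None is within 2 points of 91%. The closest is 93.2%.

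**Step 4: correlated changes.** At-least-one power at n = 55 with both scales at 1.0, from simulation of bivariate normal changes (200,000 trials per case):

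| Per-test level | corr. 0 | 0.2 | 0.5 | 0.7 |
|---|---|---|---|---|
| Two-sided 5% | 93% | 91% | 87% | 84% |
| Two-sided 2.5% | 87% | 84% | 79% | 76% |
| One-sided 5% | 97% | 96% | 93% | 91% |

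**Step 5: composite error when both true changes equal 0.75.** This counts false passes in the direction of improvement.
- Two-sided 5% per test (2.5% in that direction): 1 − 0.975² = 4.9% at correlation 0, about 4.2% at 0.7.
- Two-sided 2.5% per test: 1 − 0.9875² = 2.5% at correlation 0.
- One-sided 5% per test: 1 − 0.95² = 9.75% at correlation 0, about 8% at 0.7.

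The third level keeps 91% up to a correlation of about 0.7, but not the stated 5% error. If rejections in both directions count, two-sided 5% per test also gives 1 − 0.95² = 9.75% at correlation 0, and two-sided 2.5% per test is the level that holds 5%.

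**Step 6: one scale responds.** With one scale at 1.0 and the other at 0.75, at-least-one power is about 74% (two-sided 5%) or 64% (two-sided 2.5%).

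**The case against.** Several points on the other side have force.

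- *Against the written null there is no shortfall.* This is correct, and it is why the point is conditional. But that null does not yield 91% either, so the figure remains unexplained until the null and the threshold are reconciled.
- *The 91% is attainable.* At two-sided 5% per test it is met at a correlation of about 0.2 and exceeded at 0; at one-sided 5% it survives to about 0.7. This stands, with the composite error of about 8–10% in the one-sided case. A reader might infer that 91% is a best case needing nearly uncorrelated scales. The figures do not support that.
- *The sponsor's method is unknown.* A reader might infer independence, because 1 − (1 − 0.70)² = 0.91. But 70% per test at two-sided 5% falls at n = 50–51 (69.7% and 70.6%), not 55, and the protocol nowhere states independence. What can be shown is that the correlation is missing, not that it was set to zero.
- *A shared site and procedure do not fix the correlation.* Agreed. A common mean effect is not a within-subject correlation of changes. At 0.5 and two-sided 5% the shortfall is only 4 points.
- *Fifty-five is a floor.* Study Population Characteristics allows up to about 70 treated. At 10% attrition that is 70 × 0.9 = 63 evaluable, which gives about 91% at correlation 0.5 with two-sided 5% per test, but about 85% with two-sided 2.5%. The sample-size paragraph itself plans about 60 treated, so this cover is partial.
- *The change of 1.0 on both scales is disclosed.* True. Asking for the one-scale case is a request for a sensitivity figure, not the correction of a hidden error.

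**Conclusion.** The concern holds in a conditional form. The stated inputs do not support 91% as a free-standing figure: the written null gives essentially 100%, while a tested value of 0.75 gives a result that moves with two unstated quantities.

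At the two per-test levels that can be argued to keep the composite error at 5%, with both scales at 1.0, power over correlations 0 to 0.7 runs from 93% to 84% (two-sided 5% each) or from 87% to 76% (two-sided 2.5% each). At the second level, no non-negative correlation reaches 91%. At a correlation of 0.5, the chance of missing is 13% or 21%, against the implied 9%. If one scale responds and the other sits at 0.75, it is about 26% or 36%.

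These results rest on normally distributed changes, the sponsor's mean and SD, 55 evaluable subjects, and assumed correlations. They do not show that the trial is too small, and the issue cannot be separated from the choice of null and alpha. The plan should be corrected on this point, because its size is justified by this one number.

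**What to change.** Rewrite the sample-size paragraph, keeping 55 evaluable subjects:

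1. Reconcile the null with the 0.75 threshold, so that the tested value is stated once.
2. State the sidedness and a per-test alpha that keeps the composite error at 5%.
3. Replace the single 91% with three figures:
   - per-scale power against 0.75: 74% at two-sided 5%, or 64% at two-sided 2.5%;
   - at-least-one power at a stated planning correlation, with a range: for example, at 0.5, 87% or 79%, with 93–84% or 87–76% over 0 to 0.7;
   - power if only one scale improves by 1.0: about 74% or 64%.
4. Say how the two tests were combined, since the cited routine covers one.

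The cost is one paragraph and no extra subjects. The downside is that the stated power becomes less favourable.

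### Does giving 55/0.9 as about 60 treated subjects leave the trial short of its 55 evaluable subjects?

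*Combined protocol and SAP*

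**What the plan says.** The section Sample Size Calculation and Analysis Methods gives the requirement: "the sample size required for combined power of 91% and Type 1 error of 5% is 55". Its inputs are stated just before: "Assuming that the true change is 1.0 points on each test, and that the standard deviation (SD) is 0.7 points". It then allows for dropout: "To accommodate approximately 10% attrition, the number of subjects undergoing the procedure will be" 55/.9, followed by an approximation sign and 60.

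The Number of Subjects entry under Study Population Characteristics gives a second figure for treated subjects: "up to approximately 70 subjects treated at approximately 4-8 investigational sites in the US", with the purpose "to ensure that there are at least 55 evaluable subjects". The same entry caps enrolment at about 110.

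**The concern.** Dividing by the retained fraction is meant to protect a minimum, so the result is normally rounded up. Here 61.1 became 60, and 60 subjects at the plan's own attrition rate give 54 evaluable. The Number of Subjects entry treats 55 as a floor, so the one sentence that derives a treated number appears to miss the plan's own target. The plan also does not explain how the 60 relates to the 70 given elsewhere. If treatment really stopped at 60 and attrition ran at 10%, the primary analysis would have slightly fewer subjects than the power calculation assumed.

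**Working it through.** **Inputs.** Required evaluable number 55, attrition about 10%, treated number about 60, true change 1.0 and SD 0.7 (all from Sample Size Calculation and Analysis Methods); treated ceiling about 70 and floor of 55 evaluable (Number of Subjects).

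**The plan's own figure.** The formula N/(1 − d) is the right one. 55/(1 − 0.10) = 55/0.9 = 61.1. The stated 60 is 1.1 subjects lower, and 1.1/61.1 = 1.8%. It is the quotient taken to the nearest ten.

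**Expected evaluable number at exactly 10% attrition.**

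| Treated | Treated × 0.9 | Losses that still leave 55 | As a rate |
|---|---|---|---|
| 60 | 54.0 | 5 | 5/60 = 8.3% |
| 61 | 54.9 | 6 | 6/61 = 9.8% |
| 62 | 55.8 | 7 | 7/62 = 11.3% |
| 70 | 63.0 | 15 | 15/70 = 21.4% |

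The strict answer is 62. With 60 treated, the target holds up to 8.3% attrition. With the permitted 70 it holds up to 21.4%.

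**Cost of ending with 54 instead of 55.** The test is a one-sample t-test with SD 0.7. The plan states a null of no change, puts 0.75 in the alternative, and gives neither the sidedness nor the correlation between scales. I therefore assume a null of 0.75 (difference 1.0 − 0.75 = 0.25) and independent scales, so that power for at least one success is 1 − (1 − p)², where p is the power for one scale.

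| Alpha per scale | n | p | At least one scale |
|---|---|---|---|
| 5% two-sided | 54 | 73.1% | 92.8% |
| 5% two-sided | 55 | 73.9% | 93.2% |
| 2.5% two-sided | 54 | 62.6% | 86.0% |
| 2.5% two-sided | 55 | 63.5% | 86.7% |
| 5% one-sided | 54 | 82.8% | 97.0% |
| 5% one-sided | 55 | 83.4% | 97.3% |

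Every difference is under one percentage point. Against a null of no change, the tested difference is 1.0 and power exceeds 99.9% at both sizes. The plan's 91% is a separate matter and is not judged here.

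**Chance of reaching 55.** If each treated subject is lost independently with probability 0.10 (assumption), the binomial probability of at least 55 evaluable is 43.7% at 60 treated, 72.2% at 62 and 99.9% at 70.

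**The case for a change.** The best argument for a correction is that an approximation sign does not excuse rounding in the one direction that defeats the sentence's purpose. Neither ordinary rounding (61) nor rounding up (62) gives 60. The figure of 70 is a maximum and does not oblige the sponsor to go past 60. The binomial figures seem to strengthen this, since 60 treated reaches 55 less than half the time. The correction would also cost nothing.

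The arithmetic part stands: 62 is the right whole number at exactly 10%. The rest carries little weight. The 43.7% applies only if treatment stops at exactly 60, which the plan does not require. Under the same model, 62 treated still falls below 55 in 100% − 72.2% = 27.8% of cases. What makes 55 close to certain is the existing allowance of about 70, not a change from 60 to 62. Nor are the two treated numbers in conflict: one is worded as the planned number and the other as an upper limit, so a reader can tell them apart even though no sentence links them.

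**Conclusion.** No change is needed. The slip is real but clerical: 61.1 was written as about 60, a gap of one expected evaluable subject (54 against 55) if attrition is exactly 10%. Attrition is given only as approximate, and 60 treated still yields 55 at up to 8.3% loss. The protocol already permits about 70 treated in order to secure 55 evaluable, so the sponsor can treat 62 or more without an amendment. If the trial did end with 54, power would fall by less than one percentage point under the assumed null of 0.75 with independent scales, and by a negligible amount against the stated null of no change. No endpoint, test or conclusion depends on which number is printed. The conclusion rests on reading the 70 as available in practice, which is its stated purpose.
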